5.5 Summary of Study Data

Descriptive statistics (e.g., means, standard deviations, medians, frequencies, and percentages) will be calculated to summarize characteristics of the study arms and to identify any variables that may differ between them thus implying need for inclusion in modeling. In general, should any outcome measures have substantial departure from normality, remedial measures such as appropriate transformations or robust methods will be used for analyses.

5.6 Subject Disposition

Study status of subjects will be summarized with descriptive statistics, as described above, throughout the study. For the 12-month follow-up visit, we will summarize the number and proportion of subjects whose interview occurred, how many dropped out, were withdrawn from the study and for what reasons, and how many were lost-to-follow-up.

5.7 Protocol Deviations

Reported protocol deviations are missed visits and visits that occurred beyond the defined window period (+ 60 days from target date). We will report the total number of deviations and the frequency and percentage of each reason. Individual listings will also be produced.

5.8 Outcome Analyses

Analyses comparing demographic and clinical characteristics of the treatment arms will be assessed as follows:

Continuous variables:

- ANOVA or Mann Whitney tests will be used to compare across 3 or more groups
- *t* tests or Wilcoxon rank sum tests for comparing 2 groups

Categorical variables:

- Tests of proportions for comparing 2 groups
- χ^2 tests, or Fisher exact tests, as appropriate for the data type for 2 or more categories
- Logistic regression for interaction effects between group and given variable.

Such analyses will be used to assess baseline homogeneity of the treatment groups as well as to help us identify potential covariates to be included in linear models for assessment of outcome measures; however, clinically relevant covariates will also be included regardless of the outcomes of these analyses. All analyses will be performed in SAS 9.4.¹⁹

5.9 Baseline Descriptive Analyses

Intervention arms will be compared on baseline characteristics using descriptive statistics. Planned comparisons are for the variables described in Table 2.

5.10 Primary Outcome Analysis

5.10.1 Primary Hypotheses

5.10.1.1 Primary Hypothesis 1

We hypothesize that the Tertulias arm will have at least an 8-point decrease in depression as measured by the CES-D, from baseline to 12 months, with at least a 6.5-point greater decrease

than control participants (between arms effect size Cohen's $d = 0.43$ with SD = 15)

5.10.1.2 Primary Hypothesis 2

We hypothesize that the Tertulias arm will increase their resilience more than the control arm, from baseline to 12 months, by a Cohen's d effect size ≥ 0.33 .

5.10.1.3 Primary Hypothesis 3

We hypothesize that the Tertulias arm will decrease their social isolation more than the control arm, from baseline to 12 months, as measured by the MOS-SS with Cohen's $d \geq 0.5$.

5.10.2 Primary Analysis

Unadjusted mean changes for depression, resilience, and social support scores over time will be calculated and compared between the study arms. Linear mixed models will be fitted to the measures with the primary independent variable of interest Study Arm. **Covariates will include** age, marital status, number of children, other family or close friend living in same location as participant, speaks English, employed, and health status. The interest will be in the interaction between time point and intervention arm. Least squares mean estimates for the changes over time and their 98.3% confidence intervals will be reported for each arm. Additionally, we will report the coefficient, its standard error, and p-value for the interaction between time point and intervention arm from the linear mixed model.

Should our data assumptions of normality not be met, appropriate transformations will be identified or alternative generalized linear mixed models with alternate distributions will be fit. Our reporting will still follow as described above. We may need to use the delta method to calculate confidence intervals for point estimates on the original instrument scale.

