### Study Timeline

Study Year	Month	Activity
Year 1	1.	Hire Data Collectors, Train Staff (CITI, COI, HIPAA), Create Protocols
	2.	Create contract with local filmmaker for randomization video (a filmmaker has been identified)
	3.	Produce randomization video conclude team certifications.
	4.	Recruit for COHORT #1 Consent, Randomize & Baseline
	5.	
	6.	
	7.	COHORT #1 GROUPS
	8.	
	9.	
	10.	
	11.	
	12.	
Year 2	1.	Conduct Interviews
	2.	
	3.	
	4.	
	5.	
	6.	

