3.1 General Study Design and Plan

This is a multisite randomized controlled trial (RCT) assessing the effectiveness of the Tertulias intervention for women of Mexican origin as compared to usual care. Participants will be recruited from the community in Albuquerque, New Mexico. They must be women who are 18 years or older, speak Spanish fluently, and have income <250% of the Federal Poverty Limit. We will advertise at

community locations, focusing on two sites in Albuquerque, NM, and invite potential participants to join a live informational Zoom session to learn more about the project. If eligible and interested, the participant will be consented and randomized to one of the two arms. Within four weeks of randomization the participant will be contacted to complete the baseline interview. One year following enrollment, participants will complete a 12-month interview. See Figure 1 for the study CONSORT diagram. Primary and secondary outcomes measures are obtained from follow-up interviews.

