3.5.3 Visit Windows

Participants are randomized, and hence considered enrolled, following completion of consent and the baseline interview. The 12-month follow-up assessment occurs within a 4-week window starting at 12 months post-baseline. After the 4-week window, participants will be considered lost to follow-up.

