3.6 Description of Variables

3.6.1 Description of Outcome Variables

Table 1 describes the outcome variables and data sources.

Table 1. Outcome variables and sources

Outcome	Endpoint	Data Source
Primary Outcomes		
Depression	Difference in changes of the summed score on the Center for Epidemiologic Studies Depression Scale (CES-D) between baseline and 12 months.	Baseline and 12-month interviews
Resilience	Difference in changes of the summer score on the Connor-Davidson Resilience Scale-25 (CD-RISC 25)	Baseline and 12-month interviews
Social Support	Difference in changes of the summer score on the Social Support Scale (MOS-SSS)	Baseline and 12-month interviews
Secondary Outcomes		
Stress	(a) Difference in changes of the summer score on the Social Support Scale (MOS-SSS) (b) Change (either direction) of hair cortisol levels	(a) Baseline and 12-month interviews (b) Baseline and 12-month hair sample
Knowledge and Empowerment	Subscale summed scores on the Trauma Informed Practice Scale (TIPS)	12-month interview (Tertulias group only)
Social Network Analysis		1-month interview

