5.2 Analysis Populations

5.2.1 Intention to Treat (ITT) Population

All subjects who consented, were randomized into either arm, and completed the baseline interview are considered enrolled and comprise the ITT population. Participants who complete the informed consent, are randomized but do not complete the baseline interview will be excluded from analysis.

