5.3.1 Subgroups

This is a multisite study consisting of two sites. The data will be pooled across sites to assess the primary and secondary outcomes. Randomization is stratified by site and cohort and they will be included in all analyses as influential covariates and interaction effects between each of site and cohort with treatment arm will be assessed. Additional post-hoc subgroup analyses may be performed as exploratory analyses.

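### The primary test uses each outcome's baseline only as a repeated measure; adjusting the 12-month score for it would be more precise, provided baseline preceded known allocation

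*SAP*

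**What the plan says.** **Model.** SAP 5.10.2 fits linear mixed models to the depression, resilience and social support scores, and says: "The interest will be in the interaction between time point and intervention arm". Table 1 (SAP 3.6.1) defines the CES-D endpoint as "Difference in changes of the summed score on the Center for Epidemiologic Studies Depression Scale (CES-D) between baseline and 12 months"; the other two primary outcomes are also differences in change. SAP 5.11.2 applies the same model to the PSS-14.

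**Covariates.** SAP 5.10.2 names age, marital status, number of children, nearby family or friends, English, employment and health status. The list is not closed. Of site and cohort, SAP 5.3.1 (Subgroups) says "they will be included in all analyses as influential covariates", and SAP 5.8 says "clinically relevant covariates will also be included regardless of the outcomes of these analyses". None of these places, nor Table 2 (SAP 3.6.2), nor the statistical analysis text in Protocol 11.0, names the outcome's own baseline score. No common-baseline constraint is stated.

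**Order of baseline and allocation.**
- SAP 3.1: "Within four weeks of randomization the participant will be contacted to complete the baseline interview".
- SAP 3.5.3: "Participants are randomized, and hence considered enrolled, following completion of consent and the baseline interview".
- SAP 5.2.1: "Participants who complete the informed consent, are randomized but do not complete the baseline interview will be excluded from analysis".
- Protocol 20.0, Study Timeline: "Consent, Randomize & Baseline".
- Protocol 21.0 has women randomized at the information meeting and paid later for the baseline survey.
- Protocol 5.0 and 21.0 randomize women who have already consented, by drawing a number. Protocol 23.0 and 26.0 describe the in-person baseline appointment as the place where consent is signed, before the survey.

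SAP 3.4.2 states that the trial is unblinded.

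**The concern.** Each primary score is measured twice. When a baseline is unaffected by allocation, any arm difference in it is chance. A model with a free arm effect at baseline subtracts that chance difference in full; baseline adjustment subtracts only the part that predicts the 12-month score. The planned interaction therefore carries avoidable noise. The covariates do not remove it: entered only as main effects, they leave the interaction's precision unchanged on complete pairs.

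At stake is precision on the three primary outcomes and the PSS-14, obtainable from data that every woman in the ITT set has by definition (SAP 5.2.1). The condition matters, however. If women knew their arm when they gave the baseline interview, an arm difference there may not be chance, and the argument no longer holds.

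**Working it through.** **1. The plan's own figure.** SAP section 4 claims more than 80% power for CES-D with 100 completers per arm, 6.5 points, SD 15 and type I error 0.017. d = 6.5/15 = 0.433; noncentrality = 0.433 × √(100/2) = 3.06; two-sided critical t (198 df) = 2.407. Power is 74%, so the claim is not reproduced. One-sided 0.017 would give 82%, but the 98.3% intervals in SAP 5.10.2 are two-sided, and the protocol's MOS-SSS figure (above 86% at d = 0.5) reproduces two-sided at 87%. This discrepancy is a separate issue, used here only as a reference point.

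**2. Precision, independent women.** The correlation ρ and k (12-month SD divided by baseline SD) are not in the documents and are assumed. On complete pairs:

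variance ratio, adjusted to change = k²(1 − ρ²) / (1 + k² − 2ρk)

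At k = 1 this is (1 + ρ)/2.

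| Variance reduction | ρ = 0.7 | ρ = 0.5 | ρ = 0.3 |
|---|---|---|---|
| k = 1 | 15% | 25% | 35% |
| k = 1.2 | 3% | 13% | 24% |
| k = 0.8 | 37% | 43% | 50% |

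Simulation (20,000 trials per setting, k = 1) gave ratios of 0.85/0.755/0.65. In one simulated trial at ρ = 0.5, the interaction SE was 2.041 with or without a prognostic covariate as a main effect; adjustment for baseline gave 1.819.

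Reading SD 15 as the SD of change (the documents do not say), the planned CES-D 98.3% half-width is 2.407 × 15 × √(2/100) = 5.11 points. Multiplied by the square root of the k = 1 ratio, it becomes 4.71/4.42/4.12.

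**3. Keeping women with baseline only.** The planned mixed model can use them. With 120 enrolled (240 in two arms) and 100 complete per arm, k = 1:

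gain = [(1 − ρ)²/120] / [(1 − ρ²)/100 + (1 − ρ)²/120]

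At ρ = 0.5 this is 0.00208/0.00958 = 22%; at 0.7 and 0.3 it is 13% and 31%.

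**4. Group delivery.** Arm 2 is delivered in 12 groups (Protocol 4.0), and individual baselines do not remove group-level variance at 12 months. Assume ICC 0.05 on the single-visit variance, added in Arm 2 only. With change SD 15 and k = 1, the single-visit variance is 225/[2(1 − ρ)] = 375/225/161, so the added variance (0.05 × that, divided by 12) is 1.56/0.94/0.67.

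| | ρ = 0.7 | ρ = 0.5 | ρ = 0.3 |
|---|---|---|---|
| Change: 4.5 + added | 6.06 | 5.44 | 5.17 |
| Adjusted: 4.5(1 + ρ)/2 + added | 5.39 | 4.31 | 3.59 |
| Gain | 11% | 21% | 31% |
| Adjusted CES-D power (normal approximation) | 66% | 77% | 85% |

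Assuming independence, adjusted CES-D power would be 82/87/92%.

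**5. If baseline followed known allocation.** Take a baseline arm gap g, a share p of it persisting to 12 months, no true effect and k = 1. Bias of the change contrast is (p − 1)g; bias of ANCOVA is (p − ρ)g. With an assumed g of 0.3 SD and ρ = 0.5:

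| | Change | ANCOVA |
|---|---|---|
| Gap transient (p = 0) | −0.30 | −0.15 |
| Gap persists (p = 1) | 0.00 | +0.15 |

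ANCOVA is the less biased only when p is below (1 + ρ)/2: 65/75/85% at ρ = 0.3/0.5/0.7. A 12-month comparison without the outcome baseline has bias pg: none if the gap is transient, all of it if it persists. The common-baseline model gives the ANCOVA estimate on complete pairs, so choosing between those two protects nothing.

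**The case against.** **This is a preference.** The planned test is valid, and the change contrast is used consistently (SAP 2.2.1, 3.6.1, 5.10.1 and 5.10.2). That is why the point is graded as an improvement. It remains worth making: when baseline precedes known allocation, the adjusted estimate targets the same arm difference, is never less precise in large samples and needs no new data.

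**Changing the primary model now is risky.** This stands. Protocol 9.0 (Additional Survey Questions) reports an end-of-Y2 look at pre/post survey results by arm, which found little or no difference. A more powerful model adopted after that look needs more than an unlocked database.

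**The size is unknown.** This also stands. ρ, k and the ICC are all assumed, and the independent-women range runs from 3% to 50%.

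**The order may have been sound.** Consent signed at the baseline appointment, with only consented women randomized, suggests that in the Zoom cohorts allocation could not come before that appointment. SAP 3.1 and Protocol 21.0 point the other way. The documents do not settle it.

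**Stronger readings.** A reader might infer that the baseline scores are ignored; they are in the model as repeated outcomes. A reader might infer that the planned test is biased, or that ANCOVA is safer whichever order held; step 5 shows that neither estimator dominates if baseline followed allocation.

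**Conclusion.** The point holds as a cheap gain in precision, not as a correction of bias. The direction is firm when baseline precedes known allocation. The size is not: 15/25/35% less variance at ρ = 0.7/0.5/0.3 with equal SDs and independent women, 3/13/24% if the 12-month SD is 1.2 times baseline, and about 11/21/31% with equal SDs and an assumed ICC of 0.05.

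A reader might infer that adjustment lifts CES-D power above 80% and so repairs section 4. The documents do not support that. They give no ρ, k or ICC; at ICC 0.05 adjusted CES-D power is 66% or 77% for two of the three correlations. CD-RISC at d = 0.33 goes only from 47% to 55/61/69% even with independent women.

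If baseline followed known allocation, neither the change contrast nor ANCOVA is protected, so adjustment is not a default to adopt before the order is known.

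**What to change.** 1. **Settle the order.** Reconcile SAP 3.1, 3.5.3 and 5.2.1 with Protocol 5.0, 20.0 (Study Timeline), 21.0, 23.0 and 26.0 on whether the baseline interview preceded known allocation. Report the actual order by arm and cohort.

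2. **If it did, and the data are not locked,** amend SAP 5.10.2 (and 5.11.2 for PSS-14) to estimate the 12-month arm difference by ANCOVA on arm, own baseline score, site, cohort and the listed covariates. The equivalent common-baseline longitudinal model with covariate-by-time terms would also serve. Report a 98.3% CI (95% for PSS-14), and align SAP 2.2.1, 3.6.1 and 5.10.1. The amendment should be dated, justified independently of the end-of-Y2 look, written by someone blind to arm results, and should disclose that look. Report the planned interaction test beside it.

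3. **If baseline followed known allocation, the order cannot be established, or the data are locked,** keep the planned contrast as primary and add the baseline-adjusted estimate as a labelled sensitivity analysis. Where baseline followed or may have followed known allocation, also report a 12-month arm comparison without the outcome baseline, baseline scores by arm, and the number randomized without a baseline interview by arm. State that neither the change contrast nor ANCOVA is protected.

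On either route, correct section 4 separately.

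**Cost.** No new data: an SAP amendment or extra analyses, and disclosure of the Y2 look. SAP 5.1 sets lock at 90 days after the last interview, and Protocol 9.0 plans the last follow-up for July/August 2024; whether lock has passed must be checked. Route 3 stays open after lock.

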■) **Additional Survey Questions**. At the end of Y2, we conducted a preliminary analysis of the data. Qualitative data were extremely powerful regarding participant self-report about the importance of the intervention and the deep significance it has had on them as individuals and in their lives. These findings are clear in the data from meeting notes, interviews, evaluation discussions, and Ripple Effects Mapping sessions, and are supported by perceptions of team members who facilitate the peer support groups. However, when we analyzed the pre/post survey data using quantitative methods, there was little or no difference between the arms. It didn't seem possible that being in such an intensive intervention with reports from the participants of such deep impact could be the same as receiving nothing. So the results were not only surprising to us, they don't make sense. After much discussion with team members, our Advisory Board, individuals from the population of study, and experts in research methods, and reviewing the literature, we hypothesize that the discrepancy and lack of alignment between our qualitative and quantitative data may reflect the following: 1.) There may be some impact from the pandemic which was universally affecting participants from both arms of the study, 2.) Although the survey is conducted by 2 female Mexican immigrant data collectors, the participants do not know the data collectors—they are strangers—and this makes disclosing truthful answers to questions about mental and behavioral health (the focus of this study) challenging. There is much published data regarding the fact that in Mexican culture, people tend not to want to disclose information about mental and behavioral health (the focus of this study), and that this is particularly true for Mexican women. 3.) There is a lot of shame associated with mental and behavioral health issues in Mexican culture. 4.) Many people from the population of study do not really understand what

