3.5 Study Assessments

3.5.1 Data Collection

We will gather data through in-person data collection appointments at baseline and 12 months. Data collection appointments will be in-person in order to gather hair samples unless there are safety concerns (e.g., COVID-19 illness in the participant's home, a COVID-19-positive test within the past 2 weeks, fever, cough, travel outside the state within the past 14 days, etc.). In the case of participants with these concerns, we will conduct the survey by phone and gather the hair sample at another time if resolution of the concern is able to be made within the timeframe of a week after starting the meetings. All in-person data collection appointments will be conducted using COVID-19 safety procedures involving screening questions, temperature check, hand sanitizer, and face masks for both the data collector and the participant. Additionally, data collectors will also wear face shields, gloves, and shoe covers.

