3.5.2 Study Assessments

3.5.2.1 Baseline

We will collect basic participant characteristics such as age, marital status, education level, employment status, number of children, number of family living in their location, whether they speak English, and overall health status. Additionally, we administer the CES-D (depression), the CD-RISC (resilience), the MOS-SS (social support), and PSS (perceived stress) instruments, as well as questions about their social networks. We will also collect hair samples (see [name] et al. 2021).⁹

3.5.2.2 12-month follow-up

We will administer the CES-D (depression), the CD-RISC (resilience), the MOS-SS (social support), PSS (perceived stress), and the TIPS (empowerment) instruments (Tertulias group only). Additionally, we will ask questions about their social networks and collect hair samples.

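### The primary test is arm-by-time on two visits, but the SAP writes no time interaction for site, cohort or the baseline covariates, so as written the adjustment adds no precision and the stratification does not reach the standard error.

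*SAP*

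**What the plan says.** SAP 5.10.2 compares unadjusted mean changes between arms and then fits linear mixed models. On the target of the model it says "The interest will be in the interaction between time point and intervention arm". The covariates are "age, marital status, number of children, other family or close friend living in same location as participant, speaks English, employed, and health status". No covariate is given a time interaction, and site and cohort are not named in that section.

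The strata come in through SAP 5.3.1 (Subgroups): "Randomization is stratified by site and cohort and they will be included in all analyses as influential covariates". The same sentence goes on to say that "interaction effects between each of site and cohort with treatment arm will be assessed". Time is not mentioned there.

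There are two measurement occasions: "We will gather data through in-person data collection appointments at baseline and 12 months". The participant characteristics belong to the first of them. SAP 3.5.2.1 says "We will collect basic participant characteristics such as age, marital status, education level, employment status, number of children", and the 12-month list in SAP 3.5.2.2 does not repeat them. Site and cohort are fixed by design.

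For reporting, SAP 5.10.2 says "Least squares mean estimates for the changes over time and their 98.3% confidence intervals will be reported for each arm". For the arm-by-time term it promises the coefficient, standard error and p-value. SAP 5.11.2 applies the same analysis to PSS-14, with 95% intervals.

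**The concern.** A term that is constant within a woman and enters without time moves her baseline and 12-month scores by the same amount, so it drops out of her change. The arm-by-time coefficient is a comparison of changes. A reader of the report would be told that the primary result is adjusted for seven covariates and two stratification factors, when in complete pairs it is the unadjusted comparison.

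Cohort is the factor most likely to matter. The first cohort's groups ended in July 2021, and follow-up of the fourth was due in July/August 2024 (Protocol 9.0). Mean change may differ between years that far apart. Randomisation within cohort balances such differences between arms. If the model cannot absorb them, they stay in the residual and widen the standard error. What is at stake is precision, the accuracy of the description of the analysis, and whether the planned site and cohort checks answer the question they are meant to answer.

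**Working it through.** **Inputs.** From the documents: two visits (SAP 3.5.1); 100 completers per arm, a 6.5-point CES-D difference, SD 15 and alpha 0.017 (SAP 4); two sites (SAP 5.3.1); four cohorts (Protocol 4.0). Assumed: a random intercept for each woman, because the SAP names no covariance structure, and the spread of mean change between cohorts, for which the documents give no figure.

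**Step 1: the plan's own figure.** SE of the difference = 15 × √(2/100) = 2.121, and 6.5/2.121 = 3.06. Two-sided at 0.017, power is 75.1% (74.4% with the t distribution). One-sided it is 82.7%. The stated figure of more than 80% is therefore met only one-sided, whereas 98.3% intervals imply two-sided testing. This shortfall does not depend on the covariates and is not evidence for the present point. It only sets the starting power used below.

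**Step 2: the algebra.** Let t be 0 at baseline and 1 at 12 months, and let z hold the covariates and strata:

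Y(t) = a + b·arm + g·t + δ·arm·t + θ·z + u + e(t)

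Y(1) − Y(0) = g + δ·arm + e(1) − e(0)

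Both θ·z and u vanish. An arm × stratum term without time vanishes in the same way. It describes a difference in level that is common to both visits, not a difference in change.

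**Step 3: complete pairs, simulated.** 240 women, REML fit:

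| Fixed effects besides arm, time, arm × time | Arm-by-time | SE |
|---|---|---|
| none | −10.6326 | 2.0517 |
| covariates and strata, no time | −10.6326 | 2.0517 |
| the same plus arm × strata | −10.6326 | 2.0517 |
| with × time terms | −11.6325 | 1.8700 |

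The raw difference in mean change is also −10.6326 (SE 2.0517). In a second simulated dataset the first three fits all gave −8.589 (SE 2.085), and adding only stratum × time cut the SE to 1.964.

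**Step 4: women with baseline only kept in.** Over 200 simulated trials with dropout dependent on covariates, terms without time moved the estimate by a mean absolute 0.30 points at 16.7% dropout (maximum 1.03) and 0.58 at 33% (maximum 1.61). Mean SEs were about 2.1 and 2.5. The ratio of SEs with and without the terms averaged 1.00 (range 0.99 to 1.02).

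**Step 5: size of the loss from omitting cohort × time.** Let cohort mean changes have SD c times the residual SD. With arms balanced within cohort, the SE is inflated by about √(1 + c²): 1.020, 1.044 and 1.077 for c = 0.2, 0.3 and 0.4. Simulation gave 2.5%, 4.4% and 7.1%.

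| c (assumed) | Power without stratum × time | Power with it |
|---|---|---|
| 0 | 74.5% | 74.4% |
| 0.2 | 72.9% | 73.9% |
| 0.3 | 72.2% | 74.8% |
| 0.4 | 69.3% | 74.5% |

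The losses are 1.0, 2.6 and 5.2 points. A separate simulation gave 73%, 71% and 68% against about 74%, which is a loss of 1, 3 and 6 points. Its type I error was 0.014, 0.012 and 0.010 against the nominal 0.017.

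**The case against.** The strongest reply is that the SAP never says the terms enter only as main effects. It gives no full list of fixed effects, and it plans to assess site and cohort interactions with arm. In a model whose treatment effect is arm-by-time, a statistician could take that to mean three-way terms, which would bring stratum-by-time with them. This stands as a point about certainty. The omission is read from silence, and the wording as it is permits a model in which the strata cancel.

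Four stronger readings are tempting, and the documents do not support them.

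- *The adjustment does nothing at all.* This is exact under case deletion, and for a linear model within each imputed dataset, although covariates can still act through the imputation model. It is not exact when baseline-only women, who belong to the ITT population in SAP 5.2.1, contribute to the likelihood (step 4). Nor does it carry over in general to the generalized mixed model that SAP 5.10.2 holds in reserve.
- *The test is invalid.* The direction is conservative. There is no bias, and type I error is at or below 0.017.
- *All seven covariates need a time term.* Shrinking the SD by the variance explained makes this look attractive, but it ignores the terms that must be fitted. With 9, 12 or 15 terms fitted, simulated power was 71.7/70.6/70.1% if they explain none of the variance in change, 74.5/73.6/73.5% if they explain 5%, and 76.7/76.7/75.8% if they explain 10%. Unadjusted power was about 74 to 75%. The gain is small at best, and power can fall.
- *The team has already reported that change differs by cohort.* Protocol 9.0 says "There may be some impact from the pandemic which was universally affecting participants from both arms of the study". That remark is offered to explain why the arms looked alike in an early analysis. It says nothing about differences between cohorts.

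**Conclusion.** The concern holds as a gap in the specification of the primary model. Read as written, site, cohort and the seven covariates do not sharpen the arm-by-time comparison, the stratification by site and cohort is not reflected in its standard error, and the site-by-arm and cohort-by-arm checks do not address whether the effect on change varies.

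The consequence is modest: a standard error about 2 to 7% too large and a power loss of about 1 to 6 points. That range rests wholly on the assumed cohort spread of 0.2 to 0.4 of the residual SD. With no cohort differences the loss is nil. The cancellation itself rests on a linear model with two visits and terms without time, and it is exact for complete pairs. The point merits a correction before analysis but does not threaten the trial's validity.

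**What to change.** In SAP 5.10.2, write out the fixed effects: arm, time, arm × time, site, cohort, site × time, cohort × time, and the seven covariates. Use the same list for PSS-14. In SAP 5.3.1 (Subgroups), state that effect modification will be assessed with cohort × arm × time and site × arm × time, together with their lower-order terms, in separate models.

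Give a covariate a time term only if it is named in advance as prognostic for change. For the others, say plainly that they are not expected to add precision to the arm-by-time estimate.

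The cost is a few lines of SAP text, a small change to the code and about 4 degrees of freedom in the main model (3 for cohort × time with four cohorts, 1 for site × time with two sites) out of some 200 women. With no cohort differences, simulated power was 74.4% with these terms and 74.5% without, so the protection is nearly free. The SAP is dated June 23, 2024, before the planned fourth-cohort follow-up and the database lock, so its own timetable left room for the change. If unblinded analysis has since begun, report the revised model as a labelled sensitivity analysis.
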